4.2 Secondary Endpoints

4.2.1 Acute Success Rate

Acute success is defined as confirmation of entrance block in all PVs with an isoproterenol intravenous challenge 0.5h post procedure.

The following test subjects will be considered as acute failures:

- Entrance block not confirmed for all PVs
- Subjects in whom a non-study catheter has been used for initial ablation of any AF targets

Acute failures will be considered primary effectiveness failures. Malfunction of a non-investigational catheter during the AF procedure will not be considered an acute failure.

4.2.2 CF and Force Time Integral (FTI) for index procedure by PV segments (from PV to the atrium, divided into 3, 6, 9 and 12 point position)(as shown in the figure below)

4.2.3 Number, percentage and sites of PV reconnection for the index procedure (from PV to the atrium, divided into 3, 6, 9 and 12 point position) (as shown in the figure below)

4.2.4 Total procedural, ablation (RF) time and fluoroscopy time

4.2.5 The incidence of AEs related with the procedure and study catheter

[figure not shown]

Figure 1: Right/left pulmonary veins was divided into 3, 6, 9 and 12 point position from PV to the atrium

5.0 Treatment Description

5.1 Patient Screening

A screening log, maintained at each study site, will be used to document all subjects reviewed for potential enrolment into the study. The screening log should be completed for any patient considered for study inclusion, regardless of whether the patient is selected or not, because this will allow better management of the study enrolment rate.

Patients who sign the patient informed consent form will be considered enrolled in the study. A copy of the Patient Informed Consent template is provided. No patient should undergo any study-specific tests or exams that fall outside the standard of care without first signing the patient informed consent document for this study. An informed consent document must be obtained for a patient that is a potential study candidate prior to collection of any study related data.

5.2 Study Medications

The following medications are recommended for subjects undergoing the study catheter ablation for AF according to the 2012 CSPE Treatment Guideline FOR Atrial Fibrillation.⁵³

Medication Prior to AF Ablation Procedure

- AAD should be discontinued at least five half-lives prior to the AF ablation procedure
- Standard anticoagulation therapy is recommended prior to the AF ablation procedure

Medication During AF Ablation Procedure

- Anticoagulation therapy is recommended during the AF ablation procedure
- Isoproterenol: An isoproterenol intravenous challenge is recommended 0.5h after the CPVI procedure to confirm the entrance block and exit block.

Medication Following AF Ablation Procedure

- Standard anticoagulation therapy is recommended post ablation procedure^{12,53}

5.3 Pre-Procedure Assessments

Pre-procedure assessments should be performed prior to the index AF ablation procedure.

- To detect LA thrombi, e.g. routine TEE (Transesophageal Echocardiogram) on the day or the day before AF ablation
- ECG/ HM
- Baseline Medical history
- Arrhythmia history
- Baseline Cardiac Medications (including anticoagulation regime)

5.4 General AF Procedure Guidelines

The AF ablation procedures for this study should follow standard clinical practice guidelines⁵³.

- Diagnostic catheter placement
- Electrophysiology study (discretion of investigator)
- Transseptal puncture
- Cardioversion if subject is in AF (discretion of investigator)
- Introduction of the Study Catheter
- CARTO® 3 mapping of the targeted Left Atrium (LA)
- Ablation of targets
- An isoproterenol intravenous challenge is required 0.5h after the CPVI procedure to confirm the entrance block and exit block

In the event of spontaneous or induced AF and/or atrial flutter, the placement of additional RF lesions outside of the PV ostia is at the discretion of the investigator and includes the following:

- Ablation at sites exhibiting complex fractionated atrial electrograms (CFAE)
- Linear lesions (if linear lesions are placed, it is recommended that complete conduction block across the ablation line be demonstrated)

- Ablation for any non-PV foci in the LA and/or RA

Any sheath except Agilis can be used in conjunction with ST catheter during the procedure. Cardioversion will be allowed if deemed clinically necessary by the investigator.

5.5 Follow-up Visit Assessments

All subjects will be followed through one year after the index ablation procedure. Blanking period will span 90 days.

After the index AF ablation procedure, subject follow-up visits are required at 3 months (Day 90; 76-104 days), 6 months (Day 180; 166-210 days), 9 months (Day 270; 240-300 days), and 12 months (Day 360; 330-420 days). Follow-up visit schedule will not reset if subject undergoes a repeat AF ablation procedure with the study catheter.

At each visit, the following assessments should be performed:

- AF/AT/AFL recurrence and repeat ablation
- ECG, HM and TTM
- Current AAD (including anticoagulation regime)
- Adverse events

If a subject returns for an arrhythmia related visit outside of the protocol-defined visit schedule provided, the visit will be considered "unscheduled" (UNS). For all arrhythmia related unscheduled visits, an unscheduled visit CRF must be completed. If the unscheduled visit is for a repeat ablation procedure, the protocol follow-up schedule will be based on the index procedure.

5.6 TTM

Transtelephonic monitors (TTM) will be provided to each subject at the 3-month follow-up visit (post-blanking) for scheduled transmissions of heart rhythm status.

The TTM transmission schedule:

- Transmission will be weekly during the first 8 weeks after the blanking period (starting day 91).
- After the first 8 weeks, asymptomatic transmissions will be transmitted monthly until the end of the 12-month follow-up visit. All symptomatic arrhythmia episodes should be recorded and transmitted at the time the event occurs.

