4.0 Study Endpoints

4.1 Primary Effectiveness Endpoint

The primary effectiveness endpoint for this study is freedom from documented symptomatic atrial fibrillation (AF), atrial tachycardia (AT), or atrial flutter (AFL) episodes through 12-month follow-up after the index ablation procedure (includes a three-month blanking period).

AF/AFL/AT qualifies as an arrhythmia recurrence after the first ablation if it lasts ≥ 30 seconds and is documented by ECG, HM or TTM, etc.

The following will also be considered primary effectiveness failures and will be included in the effectiveness analysis cohorts:

- Acute procedural failure (ie, failure to confirm entrance block in all pulmonary veins with an isoproterenol intravenous challenge 0.5h post procedure or use of a non-study catheter to treat the study arrhythmia)
- A repeat ablation beyond the 90-day blanking period

Atrial tachyarrhythmia recurrence events will be recorded and included in study analysis after a 90-day blanking period; recurrence during the blanking will not be considered treatment failure; re-ablation will not be recommended during the blanking^{12,53}.

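### The TTM is handed over at the 3-month visit, allowed up to Day 104, but TTM transmissions and endpoint counting start on Day 91, so an in-window late visit leaves 1 to 13 counted days without a TTM

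*Protocol*

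**What the plan says.** **Hand-over.** Protocol 5.6: "Transtelephonic monitors (TTM) will be provided to each subject at the 3-month follow-up visit (post-blanking". The TTM row of the flow chart (Protocol 5.8; SAP 3.7, Table 1) has no entry before the 3-month column.

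**Visit window.** Protocol 5.5: "subject follow-up visits are required at 3 months (Day 90; 76-104 days". The flow chart and SAP 3.7 give the same range.

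**Use of the device.** Protocol 5.6: "Transmission will be weekly during the first 8 weeks after the blanking period (starting day 91". After those 8 weeks, "asymptomatic transmissions will be transmitted monthly until the end of the 12-month follow-up visit". Separately, "All symptomatic arrhythmia episodes should be recorded and transmitted at the time the event occurs".

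**What counts.** Protocol 4.1: "Atrial tachyarrhythmia recurrence events will be recorded and included in study analysis after a 90-day blanking period". An episode qualifies if it lasts at least 30 seconds and "is documented by ECG, HM or TTM, etc". SAP 6.5.1 plots the time to first recurrence over Days 91 to 361.

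Neither document provides for issuing the TTM before the 3-month visit, ties the weekly schedule to the actual issue date, or covers the days between Day 91 and a later in-window visit.

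**The concern.** The start of TTM transmission is a fixed day, but the hand-over is tied to a visit that may fall up to two weeks later. A visit on Days 92-104 is not a deviation, so nothing in the plan would flag the resulting gap.

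The primary endpoint is freedom from documented symptomatic recurrence. The TTM is the tool that lets a subject record an episode when symptoms start; without it, that instruction in 5.6 cannot be followed. A paroxysmal episode may end before the subject reaches an ECG or Holter. If that episode and every later one go undocumented, the subject counts as a success. Compared with holding the TTM from Day 91, the gap therefore leans towards success. The comparison is single-arm against a fixed 50% goal, so no concurrent group shares the loss. The missed routine transmissions matter less than the missing means of sending a symptomatic episode.

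**Working it through.** **Inputs.** Hand-over at the 3-month visit (Protocol 5.6); window Days 76-104 (5.5); weekly transmissions from Day 91 for 8 weeks (5.6); counting after Day 90 (4.1), plotted to Day 361 (SAP 6.5.1); 200 subjects, 65% success and 20% dropout (Protocol 8.2); subjects not followed to the endpoint counted as failures in the main analysis (SAP 6.5.1). The device is taken as usable from the day of the visit.

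**1. The plan's own figure.** SAP 6.5.4 states a minimum of 15 TTM recordings. The weekly block runs from Day 91 to 91 + 56 - 1 = Day 146, giving 8. From Day 147 to Day 360 there are 214 days; with a 30-day month (an assumption), 214/30 = 7.1, giving 7. The sum is 8 + 7 = 15, which agrees and confirms that the SAP assumes a start on Day 91.

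**2. Gap by visit day d.** Counted days without a TTM = max(0, d - 91).

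| Visit day | Counted days without TTM | First weekly slot (Days 91-97) |
|---|---|---|
| 76-91 | 0 | possible |
| 92 | 1 | possible |
| 97 | 6 | possible |
| 98 | 7 | lost |
| 104 | 13 | lost |

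The window has 104 - 76 + 1 = 29 days, of which 13 (Days 92-104) leave a gap and 7 (Days 98-104) lose the first slot.

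**3. Share of counted time.** Days 91-361 are 361 - 91 + 1 = 271 days. The largest gap is 13/271 = 4.8% of them.

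**4. Illustration in subjects.** The documents give neither the distribution of visit days nor an event rate for these days, so these assumptions are needed:

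- 20% dropout, so 0.80 × 200 = 160 subjects followed;
- 65% success among them, so 0.35 × 160 = 56 failures;
- recurrences spread evenly over the 271 days;
- every recurrence in the gap undocumented and never followed by a documented one.

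If visits are spread evenly over Days 76-104, the mean gap is (1 + 2 + ... + 13)/29 = 91/29 = 3.14 days, and 56 × 3.14/271 = 0.65 subjects (0.65/200 = 0.3 percentage points).

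If every visit is on Day 104, 56 × 13/271 = 2.7 subjects (2.7/200 = 1.3 percentage points).

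**The case against.** The strongest reply is that TTM is only one of several ways to document an episode. Protocol 4.1 accepts ECG, Holter and other records. Protocol 5.5 and 5.8 provide unscheduled arrhythmia visits with ECG and Holter and a mandatory form, so a subject with symptoms in the gap has a defined route. A late 3-month visit also brings its own ECG and 24-hour Holter after blanking. To alter the result, an episode must fall in the gap, escape all of these, and never be followed by a documented episode in the rest of the year. At the target Day 90 there is no gap at all. All of this stands, and it is why the point is minor. What remains is that clinic-based tests do not let the subject record at symptom onset, which is what 5.6 asks for.

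A reader might infer more in three ways that the documents do not support:

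- **That episodes in the gap are lost to the endpoint.** They are only less likely to be documented.
- **That late issue is what pushes a subject below the SAP's 15 recordings.** With the 12-month visit in window from Day 330 ("and 12 months (Day 360; 330-420 days"), on-time issue gives 8 + 6 = 14 by Day 330, since (330 - 146)/30 = 6.1. A count below 15 is not specific to late issue.
- **That the post-blanking remark in 5.6 settles the timing.** Read as hand-over only after Day 90, it would leave Days 91-104, and all of those except Day 91 give a gap. That reading would raise the share affected above 13 of 29; it would not close the gap.

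**Conclusion.** The point holds as a minor flaw in the monitoring schedule. A compliant subject seen on Days 92-104 has no TTM for 1 to 13 counted days (at most 4.8% of Days 91-361), and one seen on Days 98-104 also misses the first weekly transmission slot. The direction is towards success; the amount is small and cannot be computed from the documents.

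The figures of about 0.65 and 2.7 subjects are illustrations, not bounds. They overstate the effect in so far as other documentation catches the episode, the subject has a later documented episode, or some of the 56 failures are acute procedural failures that no monitor would change. They understate it if recurrence is more frequent soon after blanking than later. The documents do not support a claim that the primary conclusion would change because of this gap.

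**What to change.** Amend Protocol 5.6 so that each subject has the TTM in hand by Day 90, at discharge or by delivery, with transmissions from Day 91 as now. Adjust the TTM row of the 5.8 flow chart and SAP Table 1 if the issue point moves. Keep the 3-month window at Days 76-104; closing it earlier would push more visits, with their ECG and Holter, into blanking. With the device in hand by Day 90 the gap is zero for every permitted visit day.

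The cost is minor site logistics, a device loan longer by up to about 3 months if issued at discharge, and a small amendment that investigators must sign, with ethics committee notification or approval (Protocol 9.4.4). Endpoint, device and visits are unchanged. For devices already issued after Day 91, an optional listing of issue date and days without TTM, where the date is recorded, would show the actual size of the gap without altering the primary analysis.

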5.7 Management of Arrhythmia Recurrence During Follow-up

Repeat AF ablations(s) may be performed at the discretion of the physician in accordance with current AF management guidelines.^{11,13,32-34,53} The follow-up schedule will remain based on the initial AF ablation procedure performed with the Study Catheter. All re-ablation procedures must be fully documented in CRF.

5.8 Data Collection flow chart

	Baseline/Pre-Ablation	Ablation	Pre-Discharge	3M [Days 76-104]	6M [Days 166-210]	9M [Days 240-300]	12M [Days 330-420]	UNS ³ {as needed}
Clinic visit	X			X	X	X	X	X
Informed Consent	X							
Demographics	X							
Medical history	X							
Ablation parameter values		X						
AF status	X		X	X	X	X	X	X
Past and current Cardiac medication	X		X	X	X	X	X	X
Current anticoagulation regime	X		X	X	X	X	X	X
ECG	X		X	X	X	X	X	X
24h Holter	X			X	X	X	X	X
Examination to detect LA thrombi ¹	X							
TTM ²				X	X	X	X	X
AF/AT/AFL recurrence				X	X	X	X	X
Repeat ablation				X	X	X	X	X
Adverse events		X	X	X	X	X	X	X

1. To detect LA thrombi, e.g. routine TEE on the day or the day before AF ablation.
2. TTM transmission will be weekly during the first 8 weeks after the blanking period; After the first 8 weeks, asymptomatic transmissions will be transmitted monthly until the end of the 12-month follow-up visit. All symptomatic arrhythmia episodes should be recorded and transmitted at the time the event occurs.
3. If a subject returns for an arrhythmia related visit outside of the protocol-defined visit schedule provided, the visit will be considered "unscheduled" (UNS).

6.0 Adverse Events

6.1 Adverse Event Reporting

An adverse event (AE) is any undesirable experience (sign, symptom, illness, abnormal laboratory value, or other medical event) occurring to a subject during the course of the registry, whether or not it is related to the device or procedure. Physical findings (including

vital signs) observed at follow-up, or pre-existing physical findings that worsen compared to baseline, are adverse events if the investigator determines they are clinically significant.

6.2 Classification

6.2.1 Serious AEs

A serious adverse event is any event that meets one or more of the following criteria:

- Led to a death
- Led to a serious deterioration in the health of the subject that
 - a. Resulted in life-threatening illness or injury,
 - b. Resulted in permanent impairment of a body structure or a body function,
 - c. Required hospitalization or prolongation of existing hospitalization
 - d. Resulted in intervention such as medication or cardioversion to prevent permanent impairment of a body function or damage to a body structure, except for the treatment of a preexisting arrhythmia.
- Led to fetal distress, fetal death or a congenital abnormality or birth defect

6.2.2 Non-Serious AEs

A non-serious adverse event is any event that results in minimal transient impairment of a body function or damage to a body structure, or which does not require any intervention other than those listed under the definition of "serious adverse event".

6.2.3 Anticipated AEs

An anticipated adverse event is an event that has been reported in previous studies of radiofrequency ablation and can be decided by the investigators if it is related to the study device or procedure in this study.

The event occurs within the first week (≤ 7 days) following an AF ablation procedure with the study catheter and is one of the following: atrial perforation/ cardiac tamponade; myocardial infarction; pericarditis need to be intervened; embolism event; heart block; atrio-esophageal fistula; injury of phrenic nerve; injury of esophageal peripheral vagus nerve; acute coronary artery occlusion; vascular access complication; death, etc.

The event occurs within the first week (> 7 days) following an AF ablation procedure with the study catheter and is one of the following: arrhythmias, embolism event, death, etc.

6.2.4 Unanticipated Adverse Device Effect (UADE)

An unanticipated adverse event is a serious event not previously identified in nature, severity or degree of incidence, or any other serious problem associated with the device that relates to the rights, safety or welfare of subjects.

6.3 Reporting Requirements

The investigator must submit the completed Adverse Event Form to sponsor (or designee), any Unanticipated Adverse Device Effects (UADE) and SAEs occurring during the study, within 24 hours after becoming aware or being notified of the event, and provides additional information, if requested by JJMS.

The investigator is required to notify Local/Central EC of all SAEs and UADEs that occurred at his/her site in accordance with the Ethics Committee provisions.

The sponsor will report to all participating clinical investigators all deaths and UADEs within 5 working days after the sponsor first receives notice of the effect and/or event. The sponsor will submit every year (unless otherwise indicated by the Ethics Committee or recommended by the local regulations to all participating clinical investigators an update of all study devices related, site reported and adjudicated SAEs. A letter summarizing the study status, enrollment figures, any safety concerns will accompany the updates.

All AEs recorded must be followed until resolution or until a stable clinical endpoint is reached. If the patient is treated for an event outside the treating hospital, the site should try to obtain copies of any documentation containing pertinent information related to that specific event.

6.4 Intensity or Severity

The intensity or severity of each AE must be assessed according to the following classifications:

• Mild	Any event that results in minimal transient impairment of a body function or damage to a body structure, and/or does not require intervention other than monitoring.
• Moderate	Any event which results in moderate transient impairment of a body function or damage to a body structure, or which requires intervention, such as the administration of medication, to prevent permanent impairment of a body function or damage to a body structure.
• Severe	Any event which is life threatening, which results in permanent impairment of a body function or damage to a body structure, or which requires significant intervention, such as major surgery, to prevent permanent impairment of a body function or damage to a body structure.

6.5 Outcome

The outcome of each AE must be assessed according to the following classifications:

Resolved	Subject fully recovered with no observable residual effects.
Improved	Subject's condition improved, but residual effects remain.

Unchanged	AE is ongoing.
Worsened	Subject's overall condition worsened.
Death	Subject died as a result of the AE (whether or not the AE is related to the device or procedure).

6.6 Causality

The causality of each AE must be assessed according to the following classifications:

Device-related	The device directly caused or contributed to the AE.
Possibly Device-related	The device may have caused or contributed to the AE.
Procedure-related	The event is directly associated by timing and/or pathophysiology with the standard electrophysiology or ablation procedure described in this protocol.
Possibly Procedure-related	The AE may be associated by timing and/or pathophysiology with the standard electrophysiology procedure described in this protocol.
Not Related	The AE is not associated with either the device or the procedure described in this protocol.

6.7 Documentation

All AEs must be documented on the appropriate CRF. All AEs must be monitored until they are adequately resolved or explained. Each AE must be reported regardless of classification and seriousness, intensity, outcome or causality.

Documentation may be requested by the Sponsor, including but not limited to, a written subject narrative detailing the clinical course of the AE, a copy of any correspondence with the local Ethics Committee (EC), hospital records, and an autopsy report, if available.

7.0 PRODUCT COMPLAINTS

The post-market product complaints in this study will be submitted according to Chinese regulations. There are no specified products being investigated for this study; hence product complaint information will not be collected on eCRFs as part of this study.

Product complaints on JJMS devices must be reported to the China Complaint Handling Unit (CHU) as soon as possible (no later than 24 hours after becoming aware of the event). Reporting should follow the established local process at the site. The China CHU will ensure follow-up of the product complaint and initial reporting to the device manufacturer. The local JJMS representative must fax the Product Complaint Form to the China CHU at the following: [contact]. Subsequently, the local JJMS representative will contact the respective physician, assisting in recording the necessary details. The device should be retained, and the China CHU will assist in the collection and return of the device to

the JJMS device analysis site. It is the intent of JJMS to perform a complete evaluation of the device.

8.0 Statistical Analysis

8.1 Clinical Study Objective

The objective of this study is to assess the effectiveness and safety in the treatment for drug refractory symptomatic PAF subjects with the THERMOCOOL® SMARTTOUCH™ catheter undergoing CPVI.

